4.6.3. Laboratory Data

Clinical laboratory values will be expressed using the International System of Units (SI), except g/dL and 10⁹/L will be used for hemoglobin and nucleated erythrocytes, respectively. Values will be summarized for each clinical laboratory parameter, including hematology, clinical chemistries, and iron studies, as specified below, and in the schedule of events.

The laboratories' own reference ranges are used as the default. In the absence of these ranges, refer to the Global Reference Range (GRR) Sources identified in [Table 6](#). Age- and sex-specific ranges will be used to flag out of range values and to indicate CTCAE (version 4.03) grade, where applicable.

The versions of the GRRs being utilized for this study are footnoted below. If revised GRRs are published during the study, the version will not automatically update.

Table 6. Global Reference Range Sources

Source	Version	Purpose
Kratz A, et al. "Laboratory Reference Values". N Engl J Med. 2004;351: 1548-63.	N Engl J Med. 2004;351: 1548-63	Adult Ranges
Mayo Clinic	Updated regularly online ^[1]	Children Ranges
Brown A. NHS Blood Sciences Department of Immunology and Immunogenetics. "Immunology Age Related Reference Ranges". QPR No. IMMQ0066.	Version No. 1.4	Immunology Age-Related Reference Ranges
Shearer W, et al. "Lymphocyte subsets in health children from birth through 18 years of age: The Pediatric AIDS Clinical Trials Group P1009 study." J Allergy Clin Immunol. 2003; 112: 973-80.	J Allergy Clin Immunol. 2003; 112: 973-80.	Lymphocyte Subsets in Pediatrics ages 0 to 18

^[1]<https://www.mayocliniclabs.com/test-info/pediatric/refvalues/index.html>

Descriptive statistics on the laboratory parameters listed in [Table 7](#) below, but may not be limited to, will be presented by visit, and where applicable, change from baseline will also be provided.

Table 7. List of Laboratory Parameters

Hematology	Iron Contents

 • Complete blood count (CBC) with differential • Haptoglobin • Nucleated erythrocytes • Platelet count • Reticulocyte count • Methemoglobin • Red cell distribution width (RDW) 	
 • Iron saturation (transferrin saturation) • Serum ferritin • Serum transferrin receptor • Serum transferrin • Liver iron content • Cardiac iron content (if assessed at baseline)
Serum Chemistry and Liver Function	

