Black	Male	> 79.6	$163 \times (\text{Serum Creatinine} \times 0.011312/0.9)^{-1.209} \times (0.993)^{\text{Age}}$
White or Other	Female	≤ 61.9	$144 \times (\text{Serum Creatinine} \times 0.011312/0.7)^{0.329} \times (0.993)^{\text{Age}}$
White or Other	Female	> 61.9	$144 \times (\text{Serum Creatinine} \times 0.011312/0.7)^{-1.209} \times (0.993)^{\text{Age}}$
White or Other	Male	≤ 79.6	$141 \times (\text{Serum Creatinine} \times 0.011312/0.9)^{-0.411} \times (0.993)^{\text{Age}}$
White or Other	Male	> 79.6	$141 \times (\text{Serum Creatinine} \times 0.011312/0.9)^{-1.209} \times (0.993)^{\text{Age}}$

Note: Conversion factor for serum creatinine umol/L $\times 0.011312 = \text{mg/dL}$

- For subjects < 18 years old, Bedside-Schwartz equation for eGFR ([Schwartz et al 2019; Schwartz and Work 2019](#)) as below

Conventional:

eGFR by Schwartz = $0.413 \times (\text{Height}/\text{Enzymatic serum creatinine})$, where:

- Enzymatic serum creatinine is reported in mg/dL (x.xx)
- Height is reported in cm (x.x)

SI:

eGFR by Schwartz = $0.413 \times (\text{Height}/\text{Enzymatic serum creatinine} \times 0.011312)$, where:

- Enzymatic serum creatinine is reported in umol/L (x.xx)
- Height is reported in cm (x.x)

6.6. Statistical Methods for Confidence Interval of Percentage of Reduction in Annualized sVOE or VOE

This section presents the 1-sided of 97.5% CI for percentage reduction in annualized sVOE in the 24 months after drug product infusion from baseline. The same statistical methods will be used for the corresponding annualized number of VOE analysis.

sVOE is count outcome. Hence, it is reasonable to assume the targeted patient sub-population has an underlying distribution Poisson (λ).

Assuming the sVOE data consist of $(N_{i0}, N_{i1}, T_{i0}, T_{i1})$, $i = 1, \dots, k$, where N_{i0} and T_{i0} are the number of sVOEs and follow-up time prior to Informed Consent, serving as baseline data, respectively, and N_{i1} and T_{i1} are the number of sVOEs and follow-up time after the treatment, respectively. In Study HGB-206, $T_{i0} = 2$ years for every subject.

We assume that given λ_{i0} and λ_{i1} , $N_{i0} \sim \text{Poisson}(\lambda_{i0}T_{i0})$, and $N_{i1} \sim \text{Poisson}(\lambda_{i1}T_{i1})$ are two conditionally independent variables with a common ratio

$$r = \frac{\lambda_{i1}}{\lambda_{i0}}, i = 1, \dots, k,$$

where r is the parameter of interest. Also note that sVOE reduction can be noted as θ , where $\theta = (1 - r)$.

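### The SI form of the Bedside-Schwartz eGFR equation in SAP 6.5 lacks a pair of brackets and, as printed, returns values about 7,815 times too small

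*SAP*

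**What the plan says.** SAP Section 4.4.3.4 assigns the Schwartz formula to subjects under 18 and refers to Section 6.5 for the equations. Section 6.5 prints two forms.

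- Conventional: "eGFR by Schwartz = $0.413 \times (\text{Height}/\text{Enzymatic serum creatinine})$, where" creatinine is in mg/dL ("Enzymatic serum creatinine is reported in mg/dL (x.xx").
- SI: "eGFR by Schwartz = $0.413 \times (\text{Height}/\text{Enzymatic serum creatinine} \times 0.011312)$, where" creatinine is in umol/L ("Enzymatic serum creatinine is reported in umol/L (x.xx").

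Height is in cm in both. Between the CKD-EPI tables and the Schwartz equations a note headed "Conversion factor for serum creatinine umol/L" says that multiplying umol/L by 0.011312 gives mg/dL. The opening line of Section 6.5 sets eGFR to be reported as a whole number.

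On units, SAP Section 4.6.3 says "Clinical laboratory values will be expressed using the International System of Units (SI"; the only exceptions it names are hemoglobin and nucleated erythrocytes. Table 9 of that section gives its creatinine threshold in umol/L.

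**The concern.** The two Schwartz lines are meant to give the same eGFR for the same subject, and as printed they do not. The conversion note says that creatinine in umol/L must be multiplied by 0.011312 before it enters the equation. Creatinine is in the denominator, so the product belongs there as a whole. Without brackets the factor falls on the quotient.

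The equation feeds two planned outputs. Change from baseline in eGFR is a named secondary endpoint (SAP 1.2.6.3), summarized by group in the Transplant Population (SAP 4.4.3.4). eGFR is also in the CTCAE shift table, in the direction of decrease (SAP 4.6.3, Table 8). If adolescent values were near zero at baseline and at every later visit, the shift table could not show a decline in their renal function. Adolescents would also add changes of practically zero to the Group C summary, alongside adult changes on the proper scale.

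**Working it through.** **Inputs from the SAP (Section 6.5).** Coefficient 0.413; factor f = 0.011312, with umol/L × f = mg/dL; height H in cm; creatinine C in umol/L for the SI line.

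**Assumed inputs, not in the documents.** Adolescent height 140 to 180 cm; creatinine 0.3 to 1.0 mg/dL, which is 0.3/0.011312 = 26.5 to 1.0/0.011312 = 88.4 umol/L.

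**Step 1: is the factor itself right?** The CKD-EPI cut-points in the same section are 61.9 and 79.6 umol/L, against 0.70 and 0.90 mg/dL. 61.9 × 0.011312 = 0.700 and 79.6 × 0.011312 = 0.900. The factor agrees with the SAP's other figures, so only its placement is in question.

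**Step 2: the two readings of the SI line.**

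- As printed, normal precedence: 0.413 × (H / C) × f
- Note substituted into the conventional line: 0.413 × H / (C × f)

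The first divided by the second is f² = 0.011312² = 0.000128, and 1/f² = 7,815. H and C cancel, so this ratio does not depend on the assumed inputs.

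**Step 3: one subject, H = 160 cm, C = 53 umol/L (assumed).**

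- As printed: 0.413 × 160/53 × 0.011312 = 0.0141
- With brackets: 0.413 × 160/(53 × 0.011312) = 110.2
- Conventional line at 0.6 mg/dL: 0.413 × 160/0.6 = 110.1

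The bracketed form reproduces the conventional line; the small difference arises because 53 umol/L is 0.5995 mg/dL. The printed form does not reproduce it.

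**Step 4: the assumed range.**

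| Height, creatinine | Conventional line | SI line as printed |
|---|---|---|
| 140 cm, 1.0 mg/dL (88.4 umol/L) | 0.413 × 140/1.0 = 57.8 | 0.0074 |
| 160 cm, 0.6 mg/dL (53.0 umol/L) | 110.1 | 0.0141 |
| 180 cm, 0.3 mg/dL (26.5 umol/L) | 0.413 × 180/0.3 = 247.8 | 0.0317 |

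Every value in the last column is 0 as a whole number.

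**Step 5: effect on a change score.** A true fall from 110 to 70 is a change of −40. As printed it becomes −40 × 0.000128 = −0.005, which also reports as 0.

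**The case against.** The strongest reply is that this is a notational slip whose intent is plain. The SI line is the conventional line with creatinine replaced by creatinine × 0.011312, and the conversion note and the SI CKD-EPI rows make the same substitution. A programmer who reads the product as the denominator gets the right value. That stands. It makes the point an omission of brackets and not a mistaken conversion, but the printed rule still differs from the intended one.

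Second, the SAP does not say which Schwartz line will be programmed. Section 4.6.3 sets a convention for expressing laboratory values. Protocol 6.2.7 has these tests run by local laboratories, whose creatinine units are not given. If the conventional line is used, nothing goes wrong. This also stands: use of the SI line is a reasonable inference and no more.

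Third, literal coding would be hard to miss. All adolescent values would print as 0, baseline included, in a trial that excludes baseline eGFR below 70 (Protocol 4.3, criterion 12). That lowers the chance of an unnoticed error. It does not make the text right.

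A loss in PDF reading is unlikely. The line is set inline like the conventional one, its outer brackets are intact, and stacked fractions elsewhere in the SAP (Section 4.4.2.2) came through.

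A reader might go further and infer that adolescent eGFR results were computed wrongly, or that the trial would report kidney failure in all of them. The documents contain no results and no program, so they support neither.

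**Conclusion.** The SI Schwartz line in SAP 6.5 is wrong as printed. It is too small by a factor of 1/0.011312², about 7,815, for every height and creatinine; this rests only on the SAP's own equations and note under normal precedence. The absolute range of about 0.007 to 0.032, against about 58 to 248, rests on the assumed adolescent inputs.

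Whether it matters depends on two conditions: that the SI line is the one programmed, as the SI convention suggests, and that it is coded literally. If both hold, the eGFR change summary and the eGFR CTCAE shift table would be unusable for subjects under 18, whose number the documents do not give.

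The reach is limited. Protocol 7.4.4.3 makes the eGFR endpoint descriptive, with no test or success criterion attached. VOE-CR, sVOE-CR and Globin Response do not use eGFR. Eligibility is not touched, since exclusion criterion 12 names CKD-EPI. The adult CKD-EPI rows are outside this point: there creatinine is in the numerator of the ratio, so the factor needs no extra brackets.

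**What to change.** In SAP 6.5, rewrite the SI line as eGFR = 0.413 × Height / (enzymatic serum creatinine × 0.011312). State which unit form the derivation uses. Confirm that the derivation program gives the same value from both lines, for example with one worked case in the programming specification: 160 cm and 53 umol/L should give 110.2, and so should 160 cm with 53 × 0.011312 mg/dL in the conventional line.

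The cost is one pair of brackets, one sentence and a short program check. No data collection, sample size or hypothesis test changes.

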6.7. Search Strategy for Events of Interest

Event of Interest	Search Strategy
HIV	MedDRA HLT = Acquired immunodeficiency syndromes, Retroviral infections
Autoimmune Disease/ Immunogenicity/ long latency hypersensitivity	MedDRA HLGT = Autoimmune disorders MedDRA HLT = Autoimmunity analyses, Anaemias haemolytic immune MedDRA PT= Acute graft versus host disease, Acute graft versus host disease in intestine, Acute graft versus host disease in liver, Acute graft versus host disease in skin, Acute graft versus host disease oral, Chronic graft versus host disease, Chronic graft versus host disease in eye, Chronic graft versus host disease in intestine, Chronic graft versus host disease in liver, Chronic graft versus host disease in skin, Chronic graft versus host disease oral, Graft versus host disease, Graft versus host disease in eye, Graft versus host disease in gastrointestinal tract, Graft versus host disease in liver, Graft versus host disease in lung, Graft versus host disease in skin, Transfusion associated graft versus host disease
Malignancies	MedDRA SMQ = Malignant tumors, Malignant lymphomas, Myelodysplastic syndrome, Blood premalignant disorders
Infections	MedDRA SOC = Infections and infestations
Thromboembolic Events	MedDRA SMQ = Embolic and Thrombotic Events

